# 2. Secondary outcomes

- Number of acute attacks in preceding year, year 1 and year 2 within each group and between groups
- Number of patients with tophi at baseline, 12 months and 24 months with each group and between groups
- Mean QoL scores (overall, different domain scores of SF36 and the Gout
   Asssessment Questionnaire (GAQ) including the Gout Impact Scale (GIS) of the GAQ.
   at 0, 12 and 24 months within each group and between groups
- Mean change of QoL scores from baseline to 12 months and 24 months within each group and between groups

**Covariates and baseline predictors:** age, gender, body mass index, disease duration, tophi, associated comorbidity etc.

Task allocation and timetable: The Nottingham CTU will undertake randomisation, development of the database for RCT and the web-based data entry platform. CTU will also conduct data monitoring and quality control for the RCT data. Academic Rheumatology will recruit patients, enter the data through a web-based data entry platform for the RCT data and develop an independent database for the observational group. Both datasets are not open for any interim analysis between baseline and 24 months to keep the randomisation. Analysis will start after 24 months when the data has been fully completed, quality checked over and closed. Analysis for clinical effectiveness (efficacy and side effects) will be completed in 3 months after the closing date of the data. Analysis for cost-effectiveness will be completed in 12 months, as it requires acquisition of additional data for cost. In brief:

- Recruitment 8 months
- RCT and observation 24 months
- Results for clinical effectiveness 3 months
- Results for cost-effectiveness 12 months

Economic Analyses Plan.

Two economic analyses are planned: the first being an economic analysis alongside the RCT and the second modelling the costs and benefits over a longer time horizon. The base case in both models would use an NHS perspective, with a societal perspective (that include indirect costs such as lost productivity) being undertaken in a sensitivity analysis.

Economic analysis alongside the RCT

This analysis would simply use the costs recorded in each arm of the trial and the utility of the patients, as estimated through the SF36 and SF6-D. Costs will relate to both the interventions and the consequences of the interventions, with both direct NHS costs and indirect costs recorded. Utility will be comprised of two parts, the underlying quality of life associated with patients with gout and decrements in utility associated with a flare. Utility will be combined with quantity of life to form quality-adjusted life years (QALYs).

The incremental costs associated with the nurse-led intervention will be divided by the incremental QALY gain to form a cost per QALY ratio that can be compared with current NICE thresholds. (http://www.nice.org.uk/media/B52/A7/TAMethodsGuideUpdatedJune2008.pdf)

Modelling the costs and benefits over a longer time horizon.

It may be the case that there are larger costs associated with the initial period of the nurse-led intervention and that these becoming markedly reduced over time. Contrastingly the benefits associated with a patient managing their disease more appropriately may remain constant. As such, limiting an economic analysis to the initial 2 year period may provide an over-estimate of the true cost per QALY ratio. In order that alternative cost per QALY ratios can be calculated a mathematical model would be constructed that can model a longer time horizon. This model would be consistent with NICE's reference case.

(http://www.nice.org.uk/media/B52/A7/TAMethodsGuideUpdatedJune2008.pdf)

If appropriate from the analysis of the RCT data, subgroup analyses would be undertaken in order to assess differential cost per QALYs across different patient types.

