### Recruitment via collaborating GP surgeries

Staff at the GP's surgeries will be asked to identify patients with gout from their lists and send them a questionnaire together with covering letters from their GP practice and the CI. The questionnaire will enquire concerning their gout (including any acute attacks in the previous year), current drug treatments, comorbidities, QOL, and willingness to receive information on an additional study relating to management of gout. The questionnaire should take approximately 30 minutes to complete. Patients will be asked to return their questionnaires to Academic Rheumatology and the relevant data will be extracted to enable them to be identified as suitable for the trial. GP surgeries will be asked to send one reminder if a reply is not received within 3 weeks.

Suitable patients who indicated willingness to be informed of a management trial will be sent a letter and information sheet concerning this. Approximately 10 days after posting the information to the patient, the research team in Academic Rheumatology will telephone them to answer any questions they may have and, if they have decided they wish to participate, confirm their eligibility. If they respond positively a mutually convenient appointment will be arranged, at the patient's GP's surgery. The research nurse will inform the participant or their nominated representative (other individual or other body with appropriate jurisdiction), of all aspects pertaining to participation in the study.

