The nurse will follow up the patient at variable time intervals as appropriate to the needs of the patient. It is envisaged that visits will be most frequent (e.g. monthly) in the first 6 months when ULT is being initiated and titrated upwards; subsequently visits may reduce to 3, 6 or 9 monthly depending on difficulty of gout management. Telephone contact to review blood test results and to agree any required action can substitute for visits, and home visits for blood tests and advice are permitted if more convenient (e.g. elderly patients). If home visits are undertaken this will be done in accordance with the University of Nottingham fieldwork guidelines. If the nurse requires any advice concerning treatment strategy (e.g. in patients with serious or multiple co-morbidity, taking multiple drug treatments, or experiencing side-effects) this will be offered by Academic Rheumatology ([name] or, in his absence, another designated Rheumatologist – [name], [name] or [name]). All contacts with the patient (practice visit, home visit, telephone call) and for doctor advice will be logged (date, duration) for subsequent cost effectiveness analysis. Participants will be given a diary to keep during the 2 year study period in which they will record the date and duration of acute attacks of gout.

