### Assessment will involve:

**Enquiry:** age, sex, gout history (onset, acute attacks/frequency/sites affected/chronic symptoms), drug history (allopurinol/start date/dose, diuretics/duration; other drugs), family history comorbidities (most detailed first visit), completion of a QOL questionnaire (generic - SF36; and disease-specific - the gout assessment questionnaire (GAQ)) at the end of year one and again at the end of year 2. The questionnaires will take approximately 20 minutes to complete. Participants' blood pressure will also be checked at the end of year 2.

**Examination**: tophi (sites); height, weight (BMI).

**Investgations**: serum uric acid, GFR, creatinine.

If tophi are present, the maximum diameter of the longest tophus will be measured using a Vernier calliper and the total number and site of tophi will be recorded.

All investigations will only be undertaken to assist clinical assessment. Individuals participating in the study will receive a package of care based on current recommended quidelines.

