### **B] Control/Standard Care arm**

Participants randomised to this group will have one consultation appointment with the research nurse. At this appointment they will be assessed by the nurse (identical enquiry, examination and investigations as above) and be provided with the Arthritis Research UK gout information booklet and a diary to prospectively document their acute attacks (frequency, duration, medical advice sought, medications taken, absence from work). The discussion will focus on the management of acute attacks and not on long-term management. In addition, they will be asked to provide a blood sample to check their SUA level at baseline, 12 months and 24 months, and complete a QOL questionnaire at 12 months (a new diary will be given at this point) and 24 months. This standard care group of participants will remain under the care of their general practitioner.

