### **Secondary Efficacy Endpoints:**

Percentage in each group with reduced number of acute attacks in the second year of the study

Quality of life scores (SF36 and GAQ) at end point compared to baseline in each group and comparison of endpoint QOL scores between the two groups.

Reduction in size and number of tophi.

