# A community based randomised controlled trial comparing nurse-led intervention with standard care

# -Analysis plan

Synopsis of the design: A 2 year community based randomised controlled trial will be undertaken in Nottingham to investigate clinical effectiveness and cost-effectiveness of a nurse-led quality of care intervention versus standard of care control. A questionnaire survey will be undertaken in the GP practices in Nottinghamshire to obtain 724 patients with gout according to the American College of Rheumatology (ACR) criteria and at least one acute attack in the past year. They will be randomly allocated to the intervention and the control group using stratified (according to the participated GP practices), block (fixed block of 4 for random allocation to keep the balance between the groups) randomisation method. Participants will be examined at baseline, 12 months and 24 months for outcomes such as serum uric acid (SUA), number of acute attacks in the previous year and quality of life (QoL) (SF36).

Principles of analysis: Intention to treat (ITT) analysis will be conducted. Descriptive analysis on raw differences between groups at baseline, 12 months and 24 months will be undertaken. Multi-level regression model (MLM) will be used for the overall comparison of the treatment effect between groups with repeated measures and missing data. We shall include all data from 3 time points in the same model, with repeated measures as level 1 units and individuals as level 2 units. The treatment group and time points will be considered as covariates in the model together with covariates at baseline for the adjustment purpose. Continuous data (eg, SUA, QoL score, etc) will be analysed using MLM linear regression, whereas dichotomous and categorical data will be analysed using MLM logistic or multinomial models. Comparison will be made between the intervention and the control in the RCT, as well as between the control in the RCT and the observational group.

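### If the diary supplies years 1 and 2, within-group attack changes and any score of reduced attacks against the recalled preceding year mix true change with a change of method of unknown direction

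*Supplement*

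**What the plan says.** **Planned comparisons.** The analysis plan (17 July 2013, 2. Secondary outcomes) lists "Number of acute attacks in preceding year, year 1 and year 2 within each group and between groups". Its Principles of analysis put all three time points in one multilevel model, with repeated measures at level 1. Protocol version 8 (Secondary Efficacy Endpoints) scores the "Percentage in each group with reduced number of acute attacks in the second year of the study" and does not say what year 2 is compared with.

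**Source for the preceding year.** At recruitment, "The questionnaire will enquire concerning their gout (including any acute attacks in the previous year), current drug treatments". People who answer an advertisement are asked whether they had an attack in the last 12 months. At the first visit the nurse takes a "gout history (onset, acute attacks/frequency/sites affected/chronic symptoms"). All of these are recall.

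**Source for years 1 and 2.** In the nurse arm, "Participants will be given a diary to keep during the 2 year study period in which they will record the date and duration" of attacks. Controls receive "a diary to prospectively document their acute attacks", with a new one at 12 months. The regimen table ticks the diary for both arms. The analysis plan's synopsis, however, says participants are examined at 0, 12 and 24 months for "number of acute attacks in the previous year and quality of life (QoL) (SF36"), which could mean the same look-back question each time. No section says which instrument feeds the analysis.

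**The concern.** The diary is handed out at the nurse visit, so it cannot cover the preceding year. If it supplies years 1 and 2, every contrast between the preceding year and a study year is also a contrast between recall and diary. A participant whose attack rate never changed could then be counted as improved or worsened because the instrument changed.

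Entry also requires at least one attack in the previous year. That selects people at a relatively bad time, so the count tends to fall afterwards whatever the care and whatever the instrument.

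Two results are at stake: a statement that attacks fell within an arm, and the percentage with a reduced number in each arm if the preceding year is the reference. Attack frequency is one of the two key secondary outcomes named in the sample size section, so the choice of analysis is not peripheral.

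**Working it through.** **1. The plan's own figure.** The only number tied to this outcome is 90 per arm, from attack rates of 57% and 32%, 90% power and 5% two-sided. With mean proportion 0.445:

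n = [1.960·√(2·0.445·0.555) + 1.282·√(0.57·0.43 + 0.32·0.68)]² / 0.25² = 81.

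With the continuity correction, n = (80.94/4)·[1 + √(1 + 4/(80.94·0.25))]² = 89. The stated 90 is reproduced to within 1 and is not disputed.

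**2. Assumptions for the illustration (mine; the documents give none of these).** Attacks are Poisson with gamma-distributed personal rates, mean 1.5 or 2.5 a year, dispersion k of 1 or 3. Entry needs at least one recalled attack. Capture is the diary count expected per attack that recall would report, equal in both arms.

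**3. Regression to the mean alone.** Mean 1.5, k = 1, one method, no true change: P(0 attacks) = 0.4, so the mean recalled count at entry is 1.5/0.6 = 2.50. The mean rate in those with no attack is 1/(1/1.5 + 1) = 0.6, so entrants average (1.5 − 0.4·0.6)/0.6 = 2.10 in a later year, a fall of 16%. The same steps give 3.50 to 3.21 (mean 2.5, k = 1) and 2.98 to 2.72 (mean 2.5, k = 3), falls of 8% and 9%.

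**4. Percentage scored as reduced in year 2, no true change** (2,000,000 simulated before the entry condition):

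| Scenario | Capture 125% | 100% | 80% | 70% |
|---|---|---|---|---|
| mean 1.5, k 1 | 42.6 | 51.8 | 60.4 | 65.1 |
| mean 2.5, k 1 | 38.0 | 48.9 | 59.1 | 64.5 |
| mean 2.5, k 3 | 36.3 | 46.7 | 56.5 | 61.7 |

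The 100% column already contains regression to the mean. The other columns show what the change of method adds or removes.

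**5. Between-arm difference in percentage reduced, in points,** if the true attack rate is 40% lower in the nurse arm only:

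| Scenario | Capture 125% | 100% | 80% | 70% |
|---|---|---|---|---|
| mean 1.5, k 1 | 20.1 | 18.1 | 15.5 | 13.9 |
| mean 2.5, k 1 | 23.8 | 21.2 | 17.5 | 15.4 |
| mean 2.5, k 3 | 22.8 | 20.5 | 17.5 | 15.7 |

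**6. Alternative analysis.** With 256 · 0.9 = 230 per arm, I compared a test of percentage reduced with a Poisson model for the year-2 count (robust standard errors, log of the preceding-year count as covariate). With no treatment effect, both rejected in about 4–6% of trials at every capture. With a 25% lower rate in the nurse arm (3,000 trials per scenario):

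| Capture | Power, count model | Power, % reduced |
|---|---|---|
| 100% | 93–98% | 68–80% |
| 80% | 88–96% | 57–68% |

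The count model's rate ratio averaged 0.75 at every capture from 70% to 125%, because a capture ratio common to both arms cancels. The difference in percentage reduced did not hold still: it ran from about 9–10 points at 70% capture to 12–14 points at 125%.

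**The case against.** The strongest reply is that the change of method is inferred. No section says the diary supplies the analysed counts, the synopsis calls the outcome only self-reported, and the analysis plan's design paragraph can be read as one look-back at all three visits. On that reading the method is constant. Likewise, if year 1 is the reference for a reduced number, both counts may share one instrument. This stands, and the point is therefore conditional. It still matters, because every explicit description of on-study attack recording is a diary and no section addresses whether diary and recall are comparable.

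A second reply is that the treatment effect is defined between groups, that both arms change method together, and that time is a covariate in the model. This also stands for the year-2 counts. A reader might infer that the randomised comparison is biased, and the documents do not support that. One caveat is that the diary contents are described more fully for controls than for the nurse arm, so equal capture is an assumption.

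A reader might also infer that the change of method inflates any fall in attacks. No recall-to-diary ratio is given, and the tables show it could equally hide a fall.

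Finally, recalled history at entry is unavoidable when no diary precedes enrolment. That is so. Collecting it is no fault; the weakness lies in using it as the starting point of a before-after contrast.

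**Conclusion.** The concern holds in a conditional form. If the diary supplies years 1 and 2, the within-group comparison of the three periods cannot separate true change from change of method, and regression to the mean from the entry rule is added to both. The same applies to the reduced-number score if it is judged against the preceding year. On my assumptions, with nothing truly changed, the share scored as reduced runs from 36% to 65% as capture goes from 125% to 70%, against 47–52% with one method. Even with one instrument throughout, a within-arm fall would not be evidence that care worked.

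Under no treatment effect the between-arm comparison remains valid, given equal capture in the two arms. What depends on the method ratio is the size of the between-arm difference in percentage reduced (14–24 points for the same 40% effect). Scoring each participant as reduced or not also costs power, by about 18 to 32 points in the scenarios of step 6. The attack rates, dispersion, capture ratios and effect sizes are illustrative; the documents fix none of them.

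**What to change.** In the analysis plan, 2. Secondary outcomes:

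- Analyse year-1 and year-2 attack counts from one named instrument, the diary, between arms in a count model. The plan currently names only linear, logistic and multinomial models.
- Enter the recalled preceding-year count as a baseline covariate. Do not treat it as a repeated outcome or subtract from it.
- Make this the main attack analysis, in place of the percentage reduced against the preceding year.
- Keep within-group figures for the preceding year, year 1 and year 2 descriptive, with no claim that attacks fell within an arm.

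Do not move the reduced-number endpoint to 12-month recall to obtain a single instrument. Participants know their allocation, so recall could differ between arms, and selection on the baseline count would remain.

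The cost is wording only, with no new data collection. The downside is that the percentage reduced becomes a supporting description.

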### **Secondary endpoints:**

Percentage with reduction of frequency of acute attacks in the second year. Difference in QOL scores for SF36 and GAQ at end of study.

Percentage with reduction in size of the largest index tophus and reduction in number of tophi.

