### Power calculations:

Information that includes SUA on community-derived patients with gout is sparse. However, detailed information on frequency of attacks, treatment, SUA and quality of life is available for 250 gout patients from 17 practices in Nottingham (5, 11). In this survey: 30% of patients were on ULT; the rate for acute attacks in the previous year was 32% for patients on ULT and 57% for patients on no ULT; mean SUA was 318  $\mu$ mol/L in those taking ULT compared to 434  $\mu$ mol/L in those not taking ULT; and 23% of those taking ULT had a SUA >360  $\mu$ mol/L, compared to 75% of those not on ULT. For quality of life (SF36) overall mean and SD for those on ULT was 16.41 (2.81) compared to 15.67 (3.05) for those not on ULT, giving a pooled SD of 3.09 and a mean difference of 0.7 between groups (the latter is used as a proxy of effect size d).

According to these results, we have estimated the following sample size requirements, to achieve 90% power at 0.05% significance level, for each outcome:

- reduction in frequency of acute attacks in final year a sample size of 90 is required for each arm
  - reduction in SUA below the therapeutic target a sample size of 70 patients is required for each arm
- quality of life a sample size of 233 is required for each arm (80% power at 0.05% significance level

Allowing a 10% drop-out rate over the 2 years, this requires a total of **512 patients** (233 plus 23 dropouts in each arm) to provide adequate power for the primary outcome and for 2 of the key secondary outcomes. There are no data on changes in GAQ in response to treatment, but being a disease-specific instrument, we assume that the GAQ will be more sensitive to change than the SF36 and that a total size of 796 will be adequately powered for this outcome.

The total number of GP practices in Nottinghamshire is 170 and the estimated number of registered patients with gout is 10,720 (i.e. an average of 65 patients per GP). A questionnaire will be sent to all patients (unless they have an exclusion criterion) to detect eligible patents. A random sample of those eligible will be selected using the simple random selection after the consent to the trial.

Page **20** of **29** Final version 8 –18 May 2015

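### The quality-of-life planning text claims adequate GAQ power at 796 in a trial of 512, treats a raw 0.7-point difference as an effect size, and never says which SF36 score is the key comparison

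*Supplement*

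**What the plan says.** **Protocol version 8, Synopsis and Power calculations.** The requirement per arm is 70 for the SUA target, 90 for acute attacks and 233 for quality of life. Adding dropouts to the 233 gives 256 per arm, 512 in total.

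The quality-of-life figure comes from a survey of 250 gout patients: "overall mean and SD for those on ULT was 16.41 (2.81) compared to 15.67 (3.05) for those not on ULT". The section describes these values as "giving a pooled SD of 3.09 and a mean difference of 0.7 between groups". Of the 0.7 the text adds that "the latter is used as a proxy of effect size d". The stated requirement is "quality of life a sample size of 233 is required for each arm (80% power at 0.05% significance level".

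For the GAQ the same section says that no data exist on its response to treatment. It assumes that the GAQ is more sensitive to change than the SF36, and concludes that "a total size of 796 will be adequately powered for this outcome".

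**Protocol version 8, Secondary endpoints.** The endpoint is given as "Difference in QOL scores for SF36 and GAQ at end of study". Secondary Efficacy Endpoints likewise refers to SF36 and GAQ scores without naming one.

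**Analysis plan, Secondary outcomes.** The list reads "Mean QoL scores (overall, different domain scores of SF36 and the Gout" Assessment Questionnaire, including its Gout Impact Scale (GIS), at 0, 12 and 24 months. Mean changes from baseline follow in the next bullet. No scoring rule, range, direction or order of importance is given.

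**The concern.** Quality of life is a key secondary outcome and the one that drives recruitment: without it, 90 per arm would cover the other two. The protocol's background section also calls evidence of improved quality of life the one piece missing for a submission to the Department of Health. A reader therefore needs to know which score is meant, what difference was planned for, and whether the trial is large enough to show it. At present:

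- the GAQ power claim rests on a size the trial will not have;
- the SF36 target is described as though a raw difference were a standardised one;
- the score in which that difference is measured is not identified, so nobody can check that the planned score and the analysed score are the same.

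If the score is still open when the data are unlocked, a favourable quality-of-life result can be challenged as chosen after the fact.

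**Working it through.** **1. The GAQ size.** The stated size is 796 in total and the design size is 512 (Synopsis; Sample size). The shortfall is 796 − 512 = 284. At fixed power and significance level, the smallest detectable standardised difference varies with 1/√N. Going from 796 to 512 therefore raises it by √(796/512) = 1.25, or about 25%. The argument given does not lead to 796 either: an instrument more sensitive than the SF36 should need fewer patients than the SF36, not more.

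**2. The effect size.** Inputs from Power calculations are means 16.41 and 15.67, SDs 2.81 and 3.05, stated pooled SD 3.09 and stated difference 0.7.

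- Unrounded difference: 16.41 − 15.67 = 0.74.
- SD pooled with equal weights: √[(2.81² + 3.05²)/2] = 2.93. The stated 3.09 exceeds both group SDs, so it cannot be their pooled value.
- d from the stated figures: 0.7/3.09 = 0.227.
- d from the unrounded difference and recalculated SD: 0.74/2.93 = 0.252.

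So 0.7 is a raw difference of about 0.23 to 0.25 SD. It is not a proxy for d.

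**3. The plan's 233.** For two means, 1:1, two-sided 5% and 80% power, n per arm = 2(1.960 + 0.842)²/d².

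| d used | n per arm | Power at 233 per arm |
|---|---|---|
| 0.7 taken literally as d | 33 | above 99% |
| 0.227 (0.7/3.09) | 306 | 69% |
| 0.252 (0.74/2.93) | 247 | 78% |
| 0.26 | 233 | 80% |

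The 233 is reproduced at d = 0.26, a value the documents do not state. It does not follow from 0.7 and 3.09. Nor was 0.7 used literally as d, since that would need only 33 per arm. The calculation assumes a two-sided 5% level, as in the Synopsis; Power calculations prints 0.05%.

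**4. The score.** Four places, side by side:

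| Place | Score named |
|---|---|
| Power calculations | SF36, overall; not defined |
| Secondary endpoints | SF36 and GAQ; no score named |
| Secondary Efficacy Endpoints | SF36 and GAQ; no score named |
| Analysis plan, Secondary outcomes | overall, SF36 domains, GAQ, GIS; none ranked |

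The analysis plan alone offers at least five candidates: overall, two or more domains, GAQ and GIS. The bracket in that bullet is never closed, so it is not certain what *overall* belongs to. Nothing links any candidate to 16.41 and 15.67.

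**The case against.** The best defence has four parts.

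- **Quality of life is secondary.** The primary endpoint is the SUA target, which needs 70 per arm. This stands: nothing here touches the primary analysis.
- **The time point is already fixed.** The protocol's endpoint sections place the between-group comparison at the end of study, and the analysis plan puts all three time points in one repeated-measures model. This stands too: what is open is the score.
- **The 796 may be a leftover.** If the GAQ really is more sensitive than the SF36, 512 may suffice. That is possible, but the protocol says it has no GAQ response data, so adequacy at 512 is an assumption. The sentence as printed still relies on a number the design does not deliver.
- **N does not depend on the scale if the standardised effect carries over.** This is correct, and it is why the target should be stated as a standardised difference.

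A reader might go further and infer that the SF36 yields no overall score, that values near 16 fit none of its scales, or that the trial will lack its quality-of-life measure. The documents do not support this. They give no SF36 range or scoring rule, and the survey behind the values is cited but not shown. The regimen table has the SF36 collected at baseline, 12 and 24 months in both arms. The analysis plan lists its domain scores, and the SF6D is derived from it. What is missing is a definition and a choice, not the data.

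**Conclusion.** The concern holds as a matter of wrong figures and an unnamed score. The GAQ power claim rests on 796 patients in a trial of 512. The 0.7 called a proxy for d is about 0.23 SD on the plan's own SD, or 0.25 SD on the unrounded difference with the recalculated SD. The overall SF36 score behind 16.41 and 15.67 is undefined, and no section says which SF36 score is the key quality-of-life comparison.

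The first two points follow from the plan's figures alone; the 0.25 assumes equal weighting of the two group SDs. The third is missing specification for a secondary outcome. It matters because that outcome sized the trial. The documents do not show that the planning values are on the wrong scale, and they give no ground for preferring one SF36 score to another.

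**What to change.** In Power calculations:

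- Delete the sentence on GAQ power, or restate it for 512. With 233 per arm, 80% power and two-sided 5%, the detectable standardised difference is 0.26. No GAQ data are available to say whether that is realistic.
- Give the SF36 target as a standardised difference (about 0.23 to 0.25) and stop calling 0.7 a proxy for d. State how this target relates to the 0.26 that 233 per arm implies.
- Identify the score that produced 16.41 and 15.67, with its scoring rule and direction.

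In Secondary endpoints, Secondary Efficacy Endpoints and the analysis plan's Secondary outcomes, name one score at 24 months as the single key quality-of-life comparison. It can be the same score or another of the sponsor's choosing, with its scoring rule and direction stated. The other SF36 domains and GAQ/GIS become supportive.

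The cost is wording. The questionnaires stay as they are and nothing more is collected. The analysis plan keeps the data closed to analysis until 24-month follow-up is complete, so the choice can be made before any result is seen. The price is that the sponsor commits to one score in advance.
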